4.1 Hypothesis

The refined PF strategy will result in a higher level of implementation fidelity of ALTA (primary outcome) and improved BP control and antihypertensive medication adherence (secondary outcomes) at 12 months, compared to a self-directed control arm.

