5.1 General Design

Using a stepped-wedge cluster randomized control trial design, this study will evaluate the effect of a tailored PF strategy on the implementation of Advancing Long-term Improvements in Hypertension Outcomes through a Team-based Care Approach (ALTA), our systems-level approach to improving medication adherence and BP control, among patients with uncontrolled HTN receiving care in 10 safety-net practices in New York.

Using a mixed-methods approach, this study will be conducted in two phases: (1) a pre-implementation phase where we will refine the PF strategy, based on the Consolidated Framework for Implementation Research (CFIR) to facilitate implementation of ALTA at the practices and (2) an implementation phase, guided by Proctor's Implementation Outcomes Framework (IOF). The primary aim of the implementation phase is to evaluate, in a stepped-wedge cluster randomized trial, the level of implementation fidelity (e.g., degree to which a program is delivered, as intended) of ALTA because of the tailored PF strategies. The secondary aims are to compare the effects of PF versus usual care (UC) on BP control and medication adherence in 10 safety-net primary care practices and patients with uncontrolled HTN who are non-adherent to their antihypertensive medications. We will also explore the potential moderating factors at the practice and individual levels (e.g., organizational capacity to change, evidence-based practice attitudes) that influence level of implementation fidelity of ALTA at the practices. We will also explore the impact of ALTA on the patient-provider relationship (i.e., relationship commitment, patient-provider trust, and patient anxiety in the interaction), and determine whether any changes to the relationship also affect patients' BP control and medication adherence.

As shown in Figure 1, each participating practice will start with the UC phase and are block-randomized into four waves, with two sites per wave. The UC phase will be followed by the pre-implementation phase of 6 months, during which facilitators will conduct a practice evaluation (e.g., workflow analysis, environmental scan) based on CFIR, refine the PF strategies that will be used in the implementation phase, and train staff in the ALTA model. Following this period, sites will implement ALTA with the assistance of the facilitator for 12 months, with a 3-month follow-up period for outcome assessment.

Figure 1. Stepped wedge design of ALTA implementation

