6.1 Description of PF implementation strategy

6.1.1 Usual Care (UC) Phase

During the UC phase, patients at the sites will receive standard HTN care delivered by their primary care providers. In addition, patients and their providers will receive standard printed HTN treatment guidelines. ALTA will not be implemented at the practices during this period. During this time, bilingual RAs will recruit eligible patients into the study and collect the baseline measures at the patient, staff, and practice-levels.

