6.4.1 Statistical Design

The proposed project will evaluate, in a stepped-wedge cluster randomized controlled trial, the effect of the PF strategy on level of implementation fidelity (primary outcome) of ALTA, as well as on clinical outcomes (secondary outcomes), as compared to usual care at 12 months. Implementation fidelity will be assessed through a process evaluation using a mixed methods approach based on five core dimensions of implementation fidelity, as defined by Proctor's Implementation Outcomes Framework (described below). Clinical outcome measures include blood pressure (BP) control (defined as <140/90 mmHg) and medication adherence (assessed using the proportion of days covered [PDC] via pharmacy records). We will also examine change in systolic and diastolic blood pressure (SBP, DBP) as well as an alternate definition of BP control (<130/80 mmHg as per the new hypertension guidelines) in exploratory analyses.

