Following the NIH Best Practices for mixed methods research, we will construct a joint display that integrates the qualitative themes with the quantitative data to create a composite measure of implementation fidelity based on the five dimensions outlined above. Should the data be divergent, we will assign higher credence to the qualitative data because it provides richer explanation about participants' behaviors. We will also explore the association between implementation fidelity and the clinical outcomes. This analysis will be accomplished with a multilevel MANOVA (unstructured covariance matrix across two time points: baseline and 12 months). The analysis will have one within person factor — Time (baseline and 12-month coded naturally as months (0 and 12)) and one primary between-

patient factor (Randomization Group dummy coded as 0 = UC and 1 = PF). We will use the composite measure of implementation fidelity to predict changes in BP control and medication adherence at 12 months. We will use a 3-level analytic model to accounting for nesting in the data (observations nested within subjects nested within practices). Multilevel modeling software (SAS, Version 9, PROC MIXED) will be used to compute full information maximum likelihood (FIML) estimates of the model parameters. The PROC MIXED procedure will use an error structure that allows for the possibility of group differences in (a) the error variances at 12 months; and (b) the serial correlations of the baseline with the 12 month outcomes. The primary test is the treatment X time interaction, and the resulting F-test will provide the primary "intent to treat" test of the hypothesis. If this is statistically significant at the two tailed $\alpha=.05$ level, for ease of interpretation, we will estimate and report the magnitude of the treatment effect, with 95% CI for fidelity. Covariates will be included as necessary in adjusted analyses. All tests will be 2-sided, 0.05 level tests.

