Associations between rates of BP control and implementation fidelity will be evaluated using structural equation modeling methods. We will estimate a path model using maximum likelihood estimation to investigate relationships between BP control and implementation fidelity. Implementation fidelity will be identified as individual and simultaneous predictors of BP control. Practice-, staff-, and patient-level variables, which may influence level of implementation fidelity, will also be included in the model. In addition to the direct effects of each variable, the indirect effects from each variable to BP control via mediator variables will be estimated as the product of component direct effects and tested using bootstrapped 95% confidence intervals. Structural equation modeling analyses will be conducted using R and fit indices will be evaluated to ensure model fit.

The effect of PF on medication adherence

We will estimate similar models as BP control with PDC, calculated from available pharmacy records, as the outcome. A GLMM model using maximum likelihood estimation will be utilized to estimate the effect of PF on medication adherence with fixed effects specified for treatment phase, time, and the treatment by time interaction. We will apply any necessary transformations to the PDC outcome to improve the approximation to normality, and explore alternative regression strategies, such as rank regression and/or beta regression.

The effect of practice and individual-level moderators on implementation fidelity of ALTA

Using validated surveys (described above), we will explore potential practice-, staff- and patient-level moderators, assessing interactions between the PF strategy, level of implementation fidelity and modifiers. Potential moderators of the association between PF and implementation fidelity of ALTA will be evaluated using structural equation modeling methods. We will determine potential moderators by examining the PF x moderator interaction effects. Fit indices will be evaluated for all models to ensure adequate model fit.

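### The primary outcome, ALTA fidelity, has no informative comparator, and the test called primary does not match randomization of practices to waves

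*Combined protocol and SAP*

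**What the plan says.** The plan describes the comparison for its primary outcome in three ways.

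- Section 4.1 expects higher fidelity under practice facilitation (PF) "compared to a self-directed control arm".
- Section 6.4.1, like the study design paragraph of the synopsis, evaluates "the effect of the PF strategy on level of implementation fidelity (primary outcome) of ALTA", together with the clinical outcomes, "as compared to usual care at 12 months".
- Section 6.4.3.1 uses a between-patient factor, "Randomization Group dummy coded as 0 = UC and 1 = PF", and states that "The primary test is the treatment X time interaction". The model is introduced as an exploration of how fidelity relates to the clinical outcomes, and the fidelity composite enters as a predictor of BP control and medication adherence. The resulting F-test is nevertheless called the primary intent-to-treat test. The treatment effect, with a 95% CI for fidelity, is to be reported if that test is significant.

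On the design, Section 5.1 says that "each participating practice will start with the UC phase and are block-randomized into four waves, with two sites per wave". Six months of pre-implementation work with facilitators follow, then 12 months of ALTA with a facilitator. On usual care (UC), Section 6.1.1 says: "ALTA will not be implemented at the practices during this period".

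For moderators of fidelity, Section 6.4.3.2 says: "We will determine potential moderators by examining the PF x moderator interaction effects".

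**The concern.** A test of whether facilitation raises fidelity needs a condition in which ALTA is attempted without facilitation. The hypothesis names such a condition, but the design does not contain it. The comparator that does exist, the UC phase, is a period in which there is no ALTA to be faithful to. A fidelity contrast against that phase would favor PF however poorly ALTA was delivered, and a positive result could be read as evidence that facilitation works.

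The test labelled primary adds to the problem. Its group factor belongs to a two-arm parallel trial, its dependent variable is unclear, and it makes reporting of the fidelity estimate depend on a p-value.

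**Working it through.** There is no planned figure for fidelity to reproduce. The power statement in Section 6.4.2 (10 sites, 700 patients) concerns BP control and does not bear on this point.

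**Step 1: what value fidelity takes in usual care.** Definitions are from Sections 6.1.4 and 6.4.3.1 and Table 2.

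| Domain | Plan's measure | Value in the UC phase |
|---|---|---|
| Adherence | components rated 3, divided by 8; an absent component is rated 1 | 0/8 = 0 |
| Dose | use of ALTA components; average dose counts coaching sessions in the implementation phase | 0, or outside the definition |
| Quality | rating of ALTA coaching sessions and ALTA data entry | undefined, nothing to rate |
| Responsiveness | satisfaction with ALTA, surveyed at 12 months only | undefined |
| Differentiation | overlap of ALTA with other initiatives at the site | undefined |

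**Step 2: what a test against that zero would show.** Take the practice as the unit and compare its implementation score with its UC score of 0. If all k untied practices score above zero, the two-sided sign test gives p = 2 × 0.5^k.

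- k = 10: 2 × 0.5^10 = 0.002.
- k = 6: 2 × 0.5^6 = 0.031.

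If every practice fully implemented one component, adherence would be 1/8 = 0.125 and p would still be 0.002. The result says nothing about facilitation.

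**Step 3: whether the group factor fits the design.** The fixed effects in Section 6.4.3.1 are an intercept, group g, time t (0 or 12) and g × t, which is four columns.

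- As worded, with all practices going on to PF, g = 1 throughout. The intercept equals g, and t equals g × t, so the rank is 2.
- With g recoded as phase, and each patient measured at baseline in UC and at 12 months in implementation, there are only two distinct rows, (1, 0, 0, 0) and (1, 1, 12, 12). The rank is again 2.
- In a parallel two-arm trial there are four distinct rows, (1, 0, 0, 0), (1, 0, 12, 0), (1, 1, 0, 0) and (1, 1, 12, 12). The rank is 4.

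The model is therefore written for a parallel design. The second result assumes that no patient contributes a 12-month UC follow-up, which the documents leave unsettled (see the objection).

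**Step 4: the moderator term.** If fidelity is 0 in UC and a + b × M during implementation for a practice with moderator value M, the PF × M coefficient is b. That is the slope of fidelity on M among practices delivering ALTA. It can be estimated, but from 10 practices, and it is an association with fidelity rather than a modification of a PF effect.

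**The case against.** The case on the other side is substantial, and it limits the point in five ways.

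- A reader might infer that the trial cannot answer its primary question at all. The documents do not support that. Sections 5.1 and 5.2.1 state the primary aim and outcome as the level of fidelity, and Section 6.4.3.1 already plans component scores, dose and satisfaction compared across practices, and a mixed-methods composite. None of these needs a control. The plan also names a comparator, the UC phase; the defect is that it is uninformative for fidelity.
- A reader might infer that the group-by-time model cannot be fitted for any outcome. That is not established. Figure 1, although its table is broken in the text, appears to show later cohorts starting pre-implementation progressively later. Practices awaiting crossover could then supply 12-month UC follow-up on BP and the proportion of days covered (PDC), and the interaction could be estimated for those outcomes. Section 5.1.1, on the other hand, gives a UC phase of 3 months. The two need to be reconciled.
- A reader might infer that the PF × moderator terms are not estimable. Step 4 shows that they are, with a narrower meaning than the plan gives them.
- A reader might infer that PF and ALTA begin together. They do not: facilitators assess practices and train staff in the pre-implementation phase, before ALTA is delivered. What remains true is that no period has ALTA without PF.
- The F-test paragraph can be read as an exploratory clinical model rather than the fidelity test. That is fair to its opening sentence, but the same paragraph calls the test primary and promises an interval for fidelity. The ambiguity is itself part of the defect.

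The additional 300-patient control group does not help. It is not randomized, it comes from the same practices, and it serves the patient-provider relationship outcomes (Sections 5.3.1 and 6.4.3.3).

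**Conclusion.** The point stands in a limited form. The plan has no informative comparator for its primary outcome: the self-directed arm does not exist, and fidelity in usual care is a structural zero or undefined. The effect of facilitation over unfacilitated ALTA cannot be estimated from this design. The test called primary uses a group factor that does not match randomization of practices to waves, and it attaches a conditional report of fidelity to a model in which fidelity is a predictor.

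The defect is one of design logic, so no corrected sample size or power figure follows. Its practical size is that a PF-versus-UC test of fidelity is close to certain to succeed (p = 0.002 with ten non-zero practices) whatever facilitation contributes. This rests on the plan's own scoring rule and on the statement that ALTA is not implemented in usual care.

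BP control and PDC exist in both phases and are not affected in this way. For them the matter is one of labelling: the contrast is facilitated ALTA against usual care.

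**What to change.** 1. Reconcile the synopsis and Sections 4.1, 6.4.1 and 6.4.3.1 with Sections 5.1 and 6.1.1. Let the primary analysis estimate ALTA fidelity during the 12 implementation months, by practice and overall, with a practice-level 95% CI for the quantitative domain scores. With 10 practices the half-width is t(0.975, 9 df) × SD/√10 = 2.262/3.162 × SD = 0.715 × SD. The documents give no between-practice SD. On the 0-to-1 adherence score, assumed SDs of 0.10, 0.20 and 0.30 give half-widths of 0.07, 0.14 and 0.21. These show the precision to expect; they do not measure the defect. If a benchmark is used, state whether fidelity data had been seen when it was set, because Section 6.1.4 provides for ongoing feedback of such data to sites.
2. Remove the Randomization Group × time test as the primary test of fidelity, along with the significance condition, and always report the estimate and CI. Keep the association between fidelity and clinical outcomes as exploratory. For BP and PDC, code treatment by the practice's phase at each calendar time.
3. Describe the moderator analyses as exploratory practice-level associations with fidelity during implementation (n = 10).
4. Describe the BP and PDC contrast as PF-supported ALTA versus usual care, not as an isolated effect of PF.

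The number of practices should be settled at the same time: four waves of two sites make 8, while the plan otherwise states 10 and Figure 1 lists five cohorts. The degrees of freedom above assume 10.

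The cost is a change of wording and a narrower claim. No new data are needed.

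### Section 6.4.3.1 attaches the primary intent-to-treat label to a model that, on its natural reading, also contains implementation fidelity, a consequence of treatment with no natural value in usual care

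*Combined protocol and SAP*

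**What the plan says.** All of the following stands in one paragraph of section 6.4.3.1 (Primary Analyses).

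- Purpose: "We will also explore the association between implementation fidelity and the clinical outcomes".
- Model: "This analysis will be accomplished with a multilevel MANOVA (unstructured covariance matrix across two time points: baseline and 12 months"). It has three levels: observations within patients within practices.
- Factors: time, coded 0 and 12 months, and a between-"patient factor (Randomization Group dummy coded as 0 = UC and 1 = PF").
- Role of fidelity: "We will use the composite measure of implementation fidelity to predict changes in BP control and medication adherence at 12 months".
- Test: "The primary test is the treatment X time interaction, and the resulting F-test will provide the primary" intent-to-treat test of the hypothesis.
- Report: if that test is significant, "we will estimate and report the magnitude of the treatment effect, with 95% CI for fidelity".
- Level: "All tests will be 2-sided, 0.05 level tests".

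On usual care, section 6.1.1 says "ALTA will not be implemented at the practices during this period". Section 4.1 hypothesises that PF raises fidelity, which is the trial's primary outcome.

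Section 6.4.3.2 separately specifies models for the effect of PF on BP control and on PDC, with treatment, time and their interaction as fixed effects. Neither lists fidelity. The same section gives a path model linking fidelity to BP control, with indirect effects and bootstrapped intervals.

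**The concern.** An intent-to-treat contrast compares patients by assigned condition and must not be adjusted for something the condition brings about. Fidelity to ALTA is such a consequence: PF is meant to produce it, and it cannot be observed where ALTA is not running. With fidelity in the model as a predictor of change, the treatment-by-time term answers a different question: how much PF would change the outcome at zero fidelity. The term is also estimated poorly, because fidelity is zero throughout one condition and well above zero throughout the other, and so nearly duplicates the group indicator.

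What is at stake is the meaning of the one test in the documents labelled intent to treat. The plan would also hold two treatment-by-time tests of the same clinical outcomes, one here and one in section 6.4.3.2, with no rule for which governs if they disagree.

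**Working it through.** **1. The plan's own figure.** Section 6.4.2 states at least 80% power for a 15-point difference in BP control and over 90% for 20 points, with 10 sites, 700 patients and ICC 0.01 to 0.05. A standard stepped-wedge (Hussey-Hughes) calculation was run with a UC rate of 29% (the prior-trial rate; no planning rate is stated) and five steps. With 70 patients per site in total it gives 78.2% to 69.4% for 15 points and 95.0% to 90.1% for 20 points. With 70 per site in every period both exceed 99%. The software inputs are not given, so the 15-point figure cannot be settled, and it is not disputed here. What matters is that this calculation is for the UC-versus-implementation contrast with no fidelity term.

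**2. Value of fidelity in UC.** Under section 6.4.3.1, adherence is the number of fully implemented components divided by 8, which would be 0 in UC. Average dose is defined only over the implementation phase, so it is undefined in UC. The plan gives neither a scoring rule for the composite nor a UC value.

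**3. What the treatment-by-time term means.** With two time points, write the change as d = a + b·T + c·F, where T = 1 under PF, F is fidelity and F = 0 in UC. Then b is the treatment-by-time term and the total effect is b + c × mean(F under PF). If a share m of the total runs through fidelity, b = (1 − m) × total. For a 15-point total, b is 15, 7.5 or 0 points at m = 0, 0.5 or 1.

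**4. Precision.** With half the patients in each condition, the variance inflation of b is VIF = 1 + mean²/(2·SD²), where mean and SD describe fidelity across PF practices. All values below are assumptions.

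| Mean | SD | VIF | SE multiplier (√VIF) |
|---|---|---|---|
| 0.5 | 0.2 | 1 + 0.25/0.08 = 4.1 | 2.0 |
| 0.75 | 0.2 | 1 + 0.5625/0.08 = 8.0 | 2.8 |
| 0.7 | 0.1 | 1 + 0.49/0.02 = 25.5 | 5.0 |
| 0.75 | 0.1 | 1 + 0.5625/0.02 = 29.1 | 5.4 |

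In points, ignoring clustering, with 350 patients per condition at 29% and 44%: SE = √((0.29×0.71 + 0.44×0.56)/350) = √(0.4523/350) = 3.6 points without fidelity. With fidelity it is 3.6 × 2.0 to 3.6 × 5.4, or about 7 to 19 points.

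**5. Simulation.** 4,000 trials per row; 10 practices × (35 UC + 35 PF); change scores, so the group coefficient equals treatment by time. Assumed: total effect 0.30 SD, mean PF fidelity 0.75, UC fidelity 0.

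| Share through fidelity | Fidelity SD | Without fidelity: estimate, rejection | With fidelity: estimate, rejection | SE ratio |
|---|---|---|---|---|
| 0% | 0.1 | 0.301, 97.8% | 0.297, 10.8% | 6.24 |
| 0% | 0.2 | 0.301, 98.2% | 0.303, 23.9% | 3.43 |
| 50% | 0.1 | 0.299, 97.3% | 0.145, 6.3% | 6.21 |
| 50% | 0.2 | 0.300, 97.7% | 0.154, 9.9% | 3.45 |
| 100% | 0.1 | 0.300, 97.6% | −0.012, 5.3% | 6.22 |
| 100% | 0.2 | 0.294, 96.7% | 0.000, 5.5% | 3.42 |

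The simulated SE ratios exceed the formula's because ten sampled practices, with fidelity capped at 1, spread less than the nominal SD.

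**6. Other codings.** If UC fidelity is missing, only PF rows remain and group is constant: the design matrix has rank 2 of 3, so b is not estimable. If fidelity enters only as a time-constant main effect, it cancels from the within-patient change and treatment by time is unchanged. But such a term predicts level, whereas the plan says fidelity predicts change.

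**The case against.** The strongest reply is that the section gives no equation. Its list of factors names only time and randomisation group, and the sentence on fidelity could describe a second, later model. That is possible, and placing fidelity in the same model is an inference. It is the natural one, because the paragraph refers throughout to a single analysis and introduces no other. If two models were meant, the text still has to say which of them contains fidelity.

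The promised interval for fidelity could also mean that fidelity is the outcome of the test, in keeping with its status as primary outcome. That reading fails too: with no ALTA in UC, there is no valid baseline-to-12-month comparison of fidelity between UC and PF.

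The reply that section 6.4.3.2 already tests PF on BP control and PDC without fidelity is correct and limits the damage. The fidelity paragraph opens as exploratory, and the power calculation belongs to the fidelity-free contrast.

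A reader might infer that the labelled test removes the PF effect altogether, or that the trial has no valid test of PF on the clinical outcomes. The documents support neither. Complete removal needs three things together: a fidelity-by-time term, UC coded 0, and an effect acting wholly through fidelity. The plan states none of them. Section 4.1 does not hypothesise full mediation, and section 6.4.3.2 treats indirect effects as something to estimate.

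**Conclusion.** The point holds in a bounded form. As written, the test called intent to treat is not one: on the natural reading it is adjusted for a post-randomisation consequence of PF. Depending on coding that the plan does not give, its treatment-by-time term is reduced in proportion to the mediated share and made very imprecise, or cannot be estimated. Only a coding that does not fit the plan's own words leaves it unchanged.

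The loss of precision does not depend on mediation: with no effect running through fidelity, simulated power was still only 11-24%, against about 98% without the term. The exact sizes are illustrative. They rest on an assumed effect, an assumed mean and spread of fidelity, UC coded 0, and a linear model with no practice-level confounding of fidelity. The direction and the near-collinearity need only fidelity at zero throughout UC and well above zero, with modest spread, under PF.

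**What to change.** 1. In section 6.4.3.1, remove the primary intent-to-treat label and the wording about a confidence interval for fidelity from the fidelity-outcome analysis.
2. State that the intent-to-treat tests of PF on BP control and PDC are the models in section 6.4.3.2, and that these contain no fidelity term.
3. Make the fidelity-outcome association a separate exploratory analysis. Either restrict it to implementation-phase patients (12-month outcome on practice fidelity, adjusted for the baseline value, with a practice random effect and no treatment term), or use the existing path model and state how UC fidelity is handled there.
4. Note in the plan that practice-level fidelity supplies only 10 values, so the association will be imprecise and open to practice-level confounding.

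The cost is a change of SAP wording and at most one additional model run, with no new data or patients. It should be made before outcome results are known.
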